Statistical analysis plan

Effects of high ventilation breathwork with retention on mental health and wellbeing: A randomised placebo-controlled trial (NCT06064474)

[name], [name], [name], [name], [name]

Document date: October 09, 2023

Outcome scale measures (quantitative): Stress, anxiety, depression, mental wellbeing, sleep-related impairment, positive & negative affect, credibility & expectancy of breathwork

Primary outcome of stress at post-intervention (primary timepoint) will be calculated from Depression Anxiety Stress Scale—21 items (DASS-21) stress subscale.

Secondary outcomes of stress (at follow-up), anxiety and depression will be calculated from respective DASS-21 subscales. Scores on DASS-21 subscales will be multiplied by two to convert them to scores equivalent to longer form DASS-42 score in line with DASS scoring recommendations. Secondary outcomes of mental wellbeing and sleep-related impairment will be measured by Short Warwick-Edinburgh Mental Wellbeing Scale (SWEMWBS) and PROMIS Item Bank v. 1.0 - Sleep-Related Impairment - Short Form 4a (PROMIS-4a), respectively. Total raw scores on SWEMWBS will be transformed into metric scores using the SWEMWBS conversion table. PROMIS-4a will be scored using a T-score transformation according to the PROMIS Sleep scoring manual. Pre-intervention, post-intervention (after 21 days) and follow-up (after a further three weeks) scale score differences between groups will be analysed through mixed analysis of variance.

Secondary outcomes of positive and negative affect will be calculated from respective subscales on Positive and Negative Affect Schedule (PANAS-20). Pre-intervention, after first breathwork session, and post-intervention scale score differences between groups will be analysed through mixed analysis of variance. Self-reported credibility and expectancy of the breathwork protocol will be measured via the Credibility/Expectancy Questionnaire (CEQ-6). Descriptive statistics for all measures for all participants in each condition will be reported. Missing items within scales will be replaced using the mean for other items in the scale/subscale in cases where $\leq 30\%$ of data are missing from a scale/subscale or where whole scales/subscales are missing. Multiple imputation will be used where $> 30\%$ of data are missing from a scale/subscale or where whole scales/subscales are missing. Cronbach's alphas will be used to assess internal consistency of each scale at baseline. The DASS-21, SWEMWBS, PROMIS-4a and PANAS-20 all have one attention-check question in them to ensure participants are completing the surveys properly.

Primary analysis

Intention-to-treat; post-intervention is the primary timepoint for primary outcome stress. For both the primary outcome and secondary scale outcomes, group x time effects at the $p < .05$ level will be determined using mixed ANOVAs. Group x time effects at the $p < .05$ level will be followed up with simple contrasts (with pre-intervention as the comparator) and between-group t-tests. Baseline data will be controlled for depending on the outcome being tested (i.e., DASS-21 Stress at baseline will be entered as a covariate when testing effects on DASS-21 Stress). Data analysis will be performed in R and SPSS.

Secondary analysis

Per-protocol analysis (participants reporting at least 10 sessions of the breathwork) will be conducted as secondary analysis.

Sensitivity checks

If sizeable missing data are present at the primary timepoint of post-intervention (6% or above), they will be replaced using multiple imputation using 30 imputed datasets and entering any study variable that predict missingness or outcomes into

the imputation model, and used for sensitivity analysis. Analysis without baseline covariates will be included as sensitivity analysis. If a participant answers more than one of the attention-items incorrectly at each timepoint their data will be excluded from the main analyses but included in a sensitivity analysis.

Exploratory analysis of secondary measures

Adherence to breathwork protocol

Post-intervention, participants will answer how many times they completed the guided breathwork out of the assigned 21 days. This will be compared between groups via unpaired t-test, and correlated with outcome scale scores on DASS-21, SWEMWBS, PROMIS-4a and PANAS-20 within each condition to see whether there are any associations between adherence and changes in these scale scores. Adherence will be looked at as a moderator.

Credibility & expectancy of breathwork protocol

CEQ-6 scores will be compared between groups via unpaired t-tests. If there are significant differences between groups on credibility/expectancy, primary tests will be run again with this used in covariance analysis. Similar to adherence, CEQ-6 scores will be correlated with the outcome scale scores above, to see whether there are relationships between CEQ-6 and changes in these scale scores within each condition.

Negative side effects due to protocol

Whether participants experienced: 1) Unpleasant/unwanted short-term effects and/or 2) Lasting bad effects from the breathwork. Analysis will be content analysis.

Other outcomes (qualitative)

Below outcomes will be explored to offer complementary findings to main quantitative analyses above.

Overall Experience

Participants' perspectives and overall experience of the breathwork protocol and study-period (i.e., positive, negative, neutral, general notes, etc.) post-intervention and follow-up. At post-intervention, analysis will be sentiment analysis, based on whether a participant reported their overall experience of the breathwork as strongly positive, positive, neutral, negative, or strongly negative.

Hypothesis Guessing

Whether participants can correctly guess which condition they were allocated to, at end of follow-up questionnaire, to tentatively infer if blinding was successful.

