- Does HVBR lead to improved subjective sleep-related impairment in comparison to an active placebo control in a general population adult sample at: a) post-intervention, b) follow-up?
- Does HVBR lead to improved subjective positive affect in comparison to an active placebo control in a general population adult sample: a) immediately after the first session of breathwork, b) at post-intervention.
- Does HVBR lead to improved subjective negative affect in comparison to an active placebo control in a general population adult sample: a) immediately after the first session of breathwork, b) at post-intervention.

Exploratory Hypotheses

Additionally, we want to see if pre-post changes are correlated with a) adherence (amount of breathwork practice, i.e., is there a dose response?), and b) credibility and expectancy of the breathwork intervention given. We would expect both greater adherence (in the HVBR practice arm) and credibility/expectancy to be associated with greater improvements on the outcome measures listed. If there are significant differences between groups on credibility/expectancy then covariance analysis will be explored, to test whether differences between groups in credibility/expectancy are accounting for any measured differences in outcomes at post-intervention.

Methods

Participants

200 people (100 per group) will be recruited. We will also select the balanced sample filter option on Prolific so as to distribute the study evenly across gender. A moderate effect size, statistical power and significance level of 0.50, 0.80 and 0.05, respectively, requires a sample of 128 participants (64 per group). PsyDAO, a decentralised organisation funding research at the intersection of psychedelics and mental health, provided funding for participant payments for a sample size of 200 participants, so this was the largest sample possible, and also allows for potential attrition. The two previous published RCTs of Balban et al. (2023) and Kopplin and Rosenthal (2022) had final samples of N=108 (4 groups; HVBR condition n=33) and N=86 participants (4 groups; HVBR condition n=20), respectively. The former study was adequately powered statistically, but the latter was not (actually required a sample size of 100).

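### The SAP's missing-data rules overlap and conflict, and it does not say which data enter the primary three-wave mixed ANOVA; on one open reading, skipping follow-up removes an observed post-intervention stress score

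*SAP*

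**What the plan says.** **Item and scale rules (SAP, Outcome scale measures).** The first rule begins "Missing items within scales will be replaced using the mean for other items in the scale/subscale in cases where" and applies when up to 30% of a scale is missing. The text where it ends and the next rule starts reads "of data are missing from a scale/subscale or where whole scales/subscales are missing. Multiple imputation will be used where". The second rule then covers more than 30% missing and, again, wholly missing scales. Neither rule is tied to a particular analysis.

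**Sensitivity rule (SAP, Sensitivity checks).** "If sizeable missing data are present at the primary timepoint of post-intervention (6% or above), they will be replaced using multiple imputation". The imputation has 30 datasets, and the sentence ends "the imputation model, and used for sensitivity analysis". Missing follow-up data are not mentioned.

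**Primary analysis (SAP).** "Intention-to-treat; post-intervention is the primary timepoint for primary outcome stress". The stress ANOVA covers pre-intervention, post-intervention and "follow-up (after a further three weeks) scale score differences between groups will be analysed through mixed analysis of variance". A significant group x time effect "will be followed up with simple contrasts (with pre-intervention as the comparator) and between-group t-tests". Baseline stress is entered as a covariate.

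**Who is in the main analyses.** The only explicit rule is in the Sensitivity checks: participants who fail more than one attention item are left out of the main analyses and restored in a sensitivity analysis.

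**Attrition.** The Protocol (Participants) says of the 200 "so this was the largest sample possible, and also allows for potential attrition" and gives no rate.

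**The concern.** Two analysts could both follow this SAP, both call the result intention-to-treat, and analyse different people. One would impute every missing scale. The other would keep imputation for sensitivity analysis and run the ANOVA on participants with all three scores. Nothing prevents the choice from being made after the data are seen.

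The choice reaches the primary result because the primary question concerns post-intervention only, while the deciding test spans three waves. A conventional repeated-measures ANOVA needs every wave. On the unimputed reading, a participant whose post-intervention stress was recorded drops out of the group x time test for not returning a survey three weeks later. Simple contrasts taken from the same ANOVA lose the same people. The between-group t-tests do not need follow-up data, but they are specified only as a sequel to a significant group x time effect.

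**Working it through.** **1. The plan's own figure.** Inputs from the Protocol (Participants): standardised difference 0.50, power 0.80, significance level 0.05. Two-sided normal approximation: n per arm = 2 x (1.960 + 0.842)^2 / 0.50^2 = 62.8, so 63. The exact t-test gives power 0.7952 at 63 and 0.8015 at 64 per arm. The stated 128 reproduces. With 200 recruited, 1 - 128/200 = 36% can be lost before the sample falls to 128.

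**2. The rules side by side.**

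| Rule | Covers | Feeds |
|---|---|---|
| Mean of other items | up to 30% of a scale missing; wholly missing scales | not stated |
| Multiple imputation, no trigger | over 30% of a scale missing; wholly missing scales | not stated |
| Multiple imputation, 30 datasets | post-intervention data, if 6% or more missing | sensitivity analysis |
| Attention items | excludes participants failing more than one | main analyses |

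The first rule cannot be carried out for a wholly missing scale. If the second feeds the primary analysis, a skipped follow-up survey is a set of wholly missing scales, so it is imputed and nobody is lost; the third rule is then largely redundant. If imputation is for sensitivity only, the primary ANOVA is unimputed. The second and third rules could coexist if one meant scales skipped within a returned survey and the other meant lost surveys, but the SAP does not say so. The trigger is 0.06 x 200 = 12 people, and it ignores follow-up.

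**3. People lost on the complete-case reading (assumed rates).** Observed post-intervention scores = 200 x (1 - post loss). Three-wave completers = that number x (1 - follow-up loss among the rest).

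| Post loss | Observed post scores | Completers, 10% follow-up loss | Completers, 20% follow-up loss |
|---|---|---|---|
| 10% | 180 | 162 | 144 |
| 20% | 160 | 144 | 128 |

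**4. Type I error.** Simulation assumptions: 100 per arm, no true effect, 20% random loss at post-intervention, 20% of the rest lost at follow-up, that loss depending on post-intervention stress in the HVBR arm only, and baseline correlated 0.5 with both later waves. The test is the three-wave group x time F on completers without a baseline covariate. Entries are uncorrected / Greenhouse-Geisser, 10,000 trials.

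| Log-odds of loss per SD | Post-follow-up r = 0.5 | r = 0.7 |
|---|---|---|
| 0 | 0.0512 / 0.0508 | 0.0501 / 0.0452 |
| 0.5 | 0.0605 / 0.0596 | 0.0587 / 0.0539 |
| 1.0 | 0.0744 / 0.0729 | 0.0713 / 0.0648 |

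The Monte Carlo standard error near 5% is sqrt(0.05 x 0.95 / 10,000) = 0.0022. Allowing for this and for variation between runs, I read the results as about 5.3% to 6% (log-odds 0.5) and 6.5% to 7.5% (log-odds 1.0). At 10% follow-up loss the error is about 5% to 6%, and runs differ by about as much as the departure from 5%. The same dependence in both arms (log-odds 1.0, 20% loss) gives 0.0485 to 0.0555. A likelihood-based group x time test on all observed scores gives 0.046 to 0.049 at 20% loss.

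**5. Pre-to-post contrast.** Among completers at 20% follow-up loss it shifts by -0.050 and -0.087 SD at log-odds 0.5 and 1.0, towards HVBR when its more stressed participants are the ones who skip. The shift is +0.086 at log-odds -1.0. At 10% loss it is -0.024 and -0.045. With all post-intervention scores the rejection rate is 0.045 to 0.052.

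**6. Power.** With the test held fixed, a two-sample t-test at d = 0.5 has power 0.882 with 80 per arm and 0.801 with 64 per arm. This shows only what 32 people are worth, since the planned t-tests would not lose them.

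**The case against.** The strongest defence is that the SAP, read literally, already handles this. Its first imputation rule covers wholly missing scales with no time point, no trigger and no restriction to sensitivity analysis. A skipped follow-up falls under it, and with the intention-to-treat label nobody leaves the ANOVA. Listwise deletion is written nowhere. The stray clause in the item-mean sentence is probably a duplication that no analyst could act on. The Protocol (Procedure) pays for the surveys and sends messages for both later ones, and 200 against 128 leaves room.

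Most of this stands, and it is why the loss of endpoints is conditional. It does not remove the ambiguity. If the first rule supplied imputed data to the primary analysis, a second imputation confined to sensitivity analysis would have little purpose, so an unimputed primary analysis is equally plausible. Deleting the duplicate clause alone leaves that conflict.

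A second objection is that the main error rates omit the baseline covariate the SAP plans. That is correct, and they should be read so. With baseline as covariate and post-intervention and follow-up as the only time levels, the corresponding figures at 20% loss are 5.6% to 5.7% and 6.8% to 8.1%, so the order of magnitude is similar.

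**Conclusion.** The point holds as an unresolved conflict in the SAP that should be fixed before the data are seen. The possible harm is modest and conditional on three things: an unimputed complete-case ANOVA, appreciable follow-up loss, and loss that depends on post-intervention stress differently by arm. Where all three apply, at the assumed 20% rates, type I error is about 5.3% to 7.5% and the completer contrast shifts by about 0.05 to 0.09 SD. With random loss, or the same dependence in both arms, there is essentially no bias. All attrition rates, correlations and loss mechanisms are assumptions.

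Three stronger readings are not supported:

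- A reader might infer that the plan discards observed primary endpoints. It does not say so; that follows only on one of two open readings.
- A reader might infer much larger error rates, about 7.5% to 16.5% across the settings tried. Those belong to a baseline-adjusted post-intervention comparison restricted to follow-up completers, which the SAP does not name.
- A reader might credit data retention with a power gain of 3 to 11 points. That range comes from comparing a split-plot F on completers (0.712 to 0.909) with an unstructured-covariance test on all observed scores (0.825 to 0.971), so it also reflects a change of test. Random loss does cost some power.

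**What to change.** - Remove the reference to wholly missing scales from the item-mean sentence.
- State which missing scales each imputation rule covers (skipped within a returned survey, or whole survey lost), at which time points, and for which analysis.
- Name one primary analysis that uses every observed post-intervention score whether or not follow-up was returned. One option is a likelihood-based mixed model with baseline adjustment and a prespecified group contrast at post-intervention. The other is the planned 30-dataset imputation, extended to follow-up and including arm, baseline and observed later scores.
- Keep the complete-case mixed ANOVA as a labelled sensitivity analysis.
- Define intention-to-treat and reconcile it with the attention-check exclusion. A promise to analyse everyone randomised would contradict that exclusion unless one of them changes.

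The cost is SAP wording and a little more analysis work, since the imputation is already planned. The primary result would then rest on a missing-at-random assumption, and informative loss at post-intervention itself would remain.

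### The primary question concerns stress at post-intervention alone, but the SAP tests it through a three-occasion group x time effect and does not make one post-intervention test primary

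*SAP*

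**What the plan says.** The protocol's primary research question asks whether HVBR improves stress against placebo at post-intervention, labelled the primary timepoint. Stress at follow-up is a secondary question.

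The SAP agrees. Under Primary analysis, "post-intervention is the primary timepoint for primary outcome stress". Under the outcome scale measures, "Secondary outcomes of stress (at follow-up), anxiety and depression will be calculated from respective DASS-21 subscales".

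The test is set out differently. Scores at pre-intervention, post-intervention and "follow-up (after a further three weeks) scale score differences between groups will be analysed through mixed analysis of variance". Under Primary analysis, "For both the primary outcome and secondary scale outcomes, group x time effects at the" p < .05 level are to be judged from mixed ANOVAs, and effects at that "level will be followed up with simple contrasts (with pre-intervention as the comparator) and between-group t-tests".

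Three further sentences bear on this:
- Covariate (Primary analysis): "DASS-21 Stress at baseline will be entered as a covariate when testing effects on DASS-21 Stress".
- Sensitivity checks: "Analysis without baseline covariates will be included as sensitivity analysis".
- Credibility and expectancy: if the groups differ, "primary tests will be run again with this used in covariance analysis".

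**The concern.** The question concerns one timepoint, while the leading test covers three. A group x time effect over pre, post and follow-up asks whether the group difference changes anywhere across those occasions. It can be significant because of follow-up alone, which is secondary. It can also miss a real post-intervention difference that partly fades, because the test spends a degree of freedom on follow-up.

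The model is also unclear. Baseline stress is a level of the time factor and a covariate as well. If the covariate is taken to replace baseline as an occasion, only post and follow-up remain. Group x time then tests whether the effect differs between those two, and an effect that lasts would not register.

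Finally, the SAP does not say whether the interaction, the contrast from baseline or the t-test answers the primary question, or whether the t-test is adjusted for baseline. At stake is an analyst's choice on the primary outcome, and some power.

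**Working it through.** **Inputs from the documents.** d = 0.50, power 0.80, alpha 0.05, 128 required, 200 recruited as 100 per group (Protocol, Participants); three occasions and baseline covariate (SAP).

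**Assumed, because the documents give no values.** SD 1; equal correlation r = 0.3, 0.5 or 0.7 between occasions; follow-up effect 0, 0.25 or 0.5; complete data. The 80-per-arm rows stand for an assumed 20% loss.

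**1. The plan's own figure.** Two-sided two-sample t-test: the normal approximation gives n = 2(1.960 + 0.842)²/0.5² = 62.8 per arm. The t-based solution is 63.77, so 64 per arm and 128 in total. This reproduces. Power is 0.801 at 64 and 0.940 at 100 per arm.

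**2. Contrast and ANCOVA.** With baseline as covariate, post − pre = a + b·group + c·pre is the same model as post = a + b·group + (c + 1)·pre. The estimate b and its standard error are identical. A baseline-adjusted comparison of post means is the same test again. An unadjusted t-test is not.

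**3. Power of the post-intervention ANCOVA alone.** Effective d = 0.5/√(1 − r²) = 0.524, 0.577, 0.700 for r = 0.3, 0.5, 0.7. Power at 100 per arm: 0.958, 0.982, 0.998. At 80 per arm: 0.909, 0.952, 0.993.

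**4. Requiring group x time before the same ANCOVA.** Simulation, 40,000 trials per cell (standard error at most 0.0025), three time levels with baseline as covariate, d = 0.5 at post and 0.25 at follow-up. The ranges run from the Greenhouse-Geisser to the multivariate test, since the SAP names neither.

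| Per arm | r | ANCOVA alone | Group x time, then ANCOVA | Loss (points) |
|---|---|---|---|---|
| 100 | 0.3 | 0.958 | 0.881-0.926 | 3.2-7.7 |
| 100 | 0.5 | 0.982 | 0.950-0.963 | 1.9-3.2 |
| 100 | 0.7 | 0.998 | 0.995 | 0.3 |
| 80 | 0.3 | 0.909 | 0.779-0.850 | 5.9-13.0 |
| 80 | 0.5 | 0.952 | 0.880-0.908 | 4.4-7.2 |
| 80 | 0.7 | 0.993 | 0.979-0.982 | 1.1-1.4 |

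If the whole effect is kept at follow-up, the loss at 100 per arm is at most 1.4 points.

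**5. Effect at follow-up only (0 at post, 0.5 at follow-up), 100 per arm.** Given baseline, post and follow-up have variance 1 − r² and covariance r − r². The multivariate test has noncentrality (n/2)·0.25(1 − r²)/[(1 − r²)² − (r − r²)²].
- r = 0.3: 50 × 0.2275/0.784 = 14.5, so the interaction is significant in about 93% of trials.
- r = 0.5: 50 × 0.1875/0.5 = 18.75, about 98%.

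**6. Baseline removed as an occasion.** Group x time then tests the group difference in (post − follow-up). For a sustained effect of 0.5 its expectation is 0.5 − 0.5 = 0, so the rejection rate is the significance level, about 5%, at any sample size.

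**7. False positives at post-intervention, 100 per arm.** With an effect at follow-up only, either test named in advance gives about 5%. If either the adjusted contrast or an unadjusted t-test may count, the rate is 6.2%, 7.1% and 8.1% for r = 0.3, 0.5, 0.7. With no effect anywhere it is 2.1-2.7%. When an effect exists, the two tests disagree after a significant interaction in 1-6% of trials at 100 per arm.

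**The case against.** The ordinary reading of Primary analysis is that group x time decides and the contrasts locate the effect. The plural in "primary tests will be run again with this used in covariance analysis" fits mixed ANOVAs across several outcomes. This is a fair reading, and it tells against saying that the SAP has no decision rule. It does not rescue the rule, because a three-occasion interaction does not answer a single-timepoint question (step 5).

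The t-test need not be unadjusted. The covariate sentence makes no exception for the follow-up tests, and the analysis without baseline covariates is placed among the sensitivity checks. On that reading t-test and contrast coincide (step 2), and both the disagreement and the excess error in step 7 vanish. This stands as a possible reading. The word t-tests suggests otherwise, so the SAP should settle it.

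The precondition is inferred. The SAP does not say that post-intervention tests are omitted when group x time is not significant, and the losses in step 4 depend on that inference.

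A reader might go further and infer that the primary timepoint is undefined, that the sample size is wrong, or that the two-step rule generally inflates false positives. None of these is supported. The timepoint is explicit, 128 reproduces, and the error stays at or below about 5% for any one test named in advance.

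**Conclusion.** The concern holds as a mismatch between question and test, together with an unclear model. It should be fixed, but it is not fatal. The textual part is firm: the primary question is at post-intervention, the leading test spans three occasions, and baseline enters twice.

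The size is modest at the planned 200 and rests on assumed correlations and follow-up effects. The loss matters most with low correlation and a fading effect, and grows with attrition. The 6-8% error rate needs three things together: either test may count, the t-test is unadjusted, and an effect exists at follow-up but not at post. The SAP states no either-may-count rule. The most damaging reading is the one in step 6, where a lasting benefit would almost never be detected. The SAP does not state that reading, but its wording does not exclude it.

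**What to change.** In the SAP's Primary analysis:
- Name one primary test: ANCOVA of post-intervention DASS-21 stress on group and baseline DASS-21 stress, two-sided 0.05, with the adjusted difference and 95% CI, carried out whatever the group x time result.
- Make group x time, the follow-up contrast and any unadjusted t-test secondary.
- State that this ANCOVA is the test rerun with credibility/expectancy.

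The same post-intervention contrast from a mixed model, with post and follow-up as outcomes and baseline only as covariate, would also serve.

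The change keeps the outcome, timepoint and covariate already chosen. It costs a few sentences in the SAP, with no new data or participants and no change to the sample-size paragraph.

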
The theoretical rationale for our study is: Identifying if HVBR exerts effects on mental health and wellbeing related outcomes via a well-designed RCT within a young (18-39), healthy general population. The appropriate placebo used here may help disentangle effects of the breathwork intervention (Sevoz-Couche & Laborde, 2022), if any. The practical rationale is: Using data collected to help develop time- and cost-effective remote interventions for lowering stress and improving wellbeing. Studies included in our meta-analysis were deemed as being at moderate or high risk of bias, including all RCTs using fast breathwork, hence we plan to complete the first low risk-of-bias fast breathwork RCT. We wish to share findings through publication in a reputable open-access journal to inform practice and hopefully benefit others.

Objectives & endpoints

The main question our study attempts to address is: Does HVBR lead to improved mental health and wellbeing? Participants will be randomised to a guided audio of HVBR (four rounds with longer retentions) or placebo breathwork (15b/min with four shorter retentions) for 20min/day, for 21 days, both pre-recorded by a trained breathwork facilitator, delivered remotely. Participants will be asked whether negative effects (both short- and long-term) occurred. The study will be conducted online through Prolific (all data will be anonymous). We will collect self-reports of mental health and wellbeing pre-post and at three-week follow-up.

Research Questions

Primary research question

- Does HVBR lead to improved subjective stress (primary outcome) in comparison to an active placebo control in a general population adult sample at post-intervention (primary timepoint)?

Secondary research questions

- Does HVBR lead to improved subjective stress in comparison to an active placebo control in a general population adult sample at follow-up?
- Does HVBR lead to improved subjective anxiety in comparison to an active placebo control in a general population adult sample at: a) post-intervention, b) follow-up?
- Does HVBR lead to improved subjective depression in comparison to an active placebo control in a general population adult sample at: a) post-intervention, b) follow-up?
- Does HVBR lead to improved subjective mental wellbeing in comparison to an active placebo control in a general population adult sample at: a) post-intervention, b) follow-up?

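### Baseline stress is both a time level and a covariate with no stated time interaction, so as a main effect it leaves the group x time test unadjusted, and the route to the post-intervention comparison loses power

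*SAP*

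**What the plan says.** The Protocol's primary research question is whether the intervention improves stress "in comparison to an active placebo control in a general population adult sample at post-intervention (primary timepoint").

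The SAP's section on outcome scale measures analyses "Pre-intervention, post-intervention (after 21 days) and follow-up (after a further three weeks) scale score differences between groups" by mixed analysis of variance, so pre-intervention is one of three time levels. For PANAS-20 the three levels are "Pre-intervention, after first breathwork session, and post-intervention scale score differences between groups".

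Under Primary analysis, the test is group x time at the 5% level. A significant result at that "level will be followed up with simple contrasts (with pre-intervention as the comparator) and between-group t-tests". The next sentence adds the covariate: "DASS-21 Stress at baseline will be entered as a covariate when testing effects on DASS-21 Stress". No model formula is given; the SAP says only "Data analysis will be performed in R and SPSS". Under Sensitivity checks: "Analysis without baseline covariates will be included as sensitivity analysis".

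The Protocol's Participants section says "200 people (100 per group) will be recruited". It gives 128 (64 per group) as the number needed for an effect of 0.50 with power 0.80 at the 0.05 level.

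**The concern.** The same score is an outcome at the first time level and a predictor of the outcome at all three. What the covariate does then depends on a term that the SAP does not mention, baseline x time. Without it, the promised baseline control does not reach the test that decides the primary outcome, and one sensitivity analysis becomes a copy of that test. With it, the post-versus-pre group contrast is an ordinary analysis of covariance (ANCOVA).

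The route to the answer adds to this. The Protocol asks about one visit. The SAP reaches that visit through an omnibus test over three, followed by t-tests with no stated covariate. At stake are power, precision, and which number is reported as the primary result.

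**Working it through.** **Plan's own figure.** A two-sided two-sample t-test at effect 0.5, power 0.80 and alpha 0.05 needs 63.77 per arm by the noncentral t, so 64 per arm and 128 in total. The stated figure reproduces. It describes one unadjusted comparison at one visit, with no gate and no covariate. That t-test alone has power 80.1% at 64 per arm and 94.0% at 100.

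**Why the main effect cancels.** Write person i's score at time t as m_t + g_t·G + b·B + person effect + error, with G the group and B the baseline score. Subtracting pre from post removes b·B, which leaves (g_post − g_pre)·G. The covariate has no influence on this contrast or on any other part of group x time. If the slope varies with time (b_t), the model fits pre exactly (b_pre = 1, g_pre = 0), and the contrast equals the ANCOVA of post on group and baseline.

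Check on one simulated dataset (100 per arm, correlation 0.5): F(2,396) = 6.815 with no covariate and 6.815 with a main-effect covariate; F(2,394) = 8.827 with baseline x time. The crossed contrast and the ANCOVA were both −0.494 (SE 0.118).

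**Precision at post-intervention, 100 per arm, unit SD.** The pre-post correlation r is not in the documents; 0.3/0.5/0.7 is assumed, equal between all visits.

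| Estimate | SE formula | SE (SD units) |
|---|---|---|
| Post-versus-pre contrast, main-effect covariate | sqrt(0.02 × 2(1−r)) | 0.167/0.141/0.110 |
| Raw t-test | sqrt(0.02) | 0.141 |
| Model-based post difference, main-effect covariate | sqrt(0.02 × (1+b²−2br)), b = (1+2r)/3 | 0.139/0.125/0.102 |
| Baseline-adjusted (crossed or ANCOVA) | sqrt(0.02 × (1−r²)) | 0.135/0.122/0.101 |

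**Power.** 40,000 simulated trials per cell, complete data, effect 0.5 at both later visits, univariate repeated-measures F for group x time, all tests at 5%; results for r = 0.3/0.5/0.7.

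| Route | 100 per arm | 64 per arm |
|---|---|---|
| Group x time, main-effect covariate | 88/96/99.8% | 69/83/97% |
| That gate, then raw t-test | 83/91/94% | 58/69/78% |
| Group x time, crossed covariate | 98/99/99.9% | 85/92/99% |
| Crossed gate, then raw t-test | 93/94/94% | 75/78/80% |
| Crossed gate, then adjusted contrast | 94/98/99.8% | 77/87/97% |
| Adjusted difference tested directly | 96/98/99.8% | 83/90/97% |

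The two codings disagree on whether group x time is significant in about 11/3/0.1% of trials at 100 per arm and 22/12/2% at 64. With no effect, group x time rejects in 4.9–5.3% of trials under either coding.

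Two losses are visible. At r = 0.3 the unadjusted gate costs most. At r = 0.7 the gate almost always passes and the raw t-test is the limit, because it cannot exceed 94% (80% at 64 per arm) whatever the correlation.

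**The case against.** The strongest reply is that crossing is what the authors mean. The analysis without baseline covariates would otherwise be empty, and the sentence on baseline control can be read as covering the follow-up tests too. Crossing is indeed the more likely intent. But the text does not state it, and under crossing a raw t-test would still leave the reported difference unadjusted. A further reading, that pre-intervention leaves the time factor once it becomes a covariate, fits poorly with contrasts against pre-intervention.

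Second, a main-effect covariate is not inert everywhere. It does adjust the model-based group difference at post-intervention, whose SE is within about 3% of the crossed model's. This stands: the change-score SE belongs only to the post-versus-pre contrast. However, the SAP names contrasts and t-tests, not that model-based difference.

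Third, the planned case is comfortable: group x time has at least 88% power under either coding. The 64-per-arm figures would need a 36% loss from 100 (36/100), which the documents do not predict. Part of the gap is also the price of requiring two significant results: with no effect at all, the main-effect gate and raw t-test are both significant in only about 1.2/0.8/0.6% of trials, against about 5% for the direct test. All of this is fair, and it keeps the point below a question of validity.

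A reader might infer that the result would be biased, that false positives are inflated, or that the sample size is wrong. None of these follows: randomisation protects both codings, each holds its 5% level, and 128 is correct for the comparison it describes. A reader might also infer that the SAP's gate has almost no power. That would be true only if pre-intervention were removed from the time factor, and the SAP keeps it as the comparator.

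**Conclusion.** The point holds as a specification gap with a measurable cost in power and precision, and it should be fixed. Taken as a main effect, the baseline covariate does nothing for the group x time test or the post-versus-pre contrast. The gate followed by a raw t-test then gives up about 12/8/6 percentage points at 100 per arm, and about 25/21/19 at 64 per arm, against the adjusted difference tested directly (for example 95.5 − 83.1 = 12.4 and 83.3 − 58.2 = 25.1 at r = 0.3). If the covariate is crossed and the adjusted contrast is reported, the loss at 100 per arm is about one point or less. The choice of coding and of follow-up test therefore decides the size.

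These figures rest on assumed correlations of 0.3 to 0.7, complete data, equal correlation between visits and the same effect at both later visits. The cancellation itself needs only complete data.

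**What to change.** Name the baseline-adjusted group difference in DASS-21 stress at post-intervention, with its 95% CI, as the primary estimate. Test it directly at p<.05, in place of the group x time gate and raw t-test. Write out the model, using either of these forms:

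1. Keep three time levels, state that baseline x time is included, and take the adjusted post-versus-pre group contrast with its own error term.
2. Model post-intervention and follow-up only, on group, time, group x time, baseline and baseline x time. Here the group x time gate must be dropped, because it tests only whether the effect differs between the two later visits. With an equal 0.5 benefit at both it would reject in only about 5% of trials.

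Both forms give the same post-intervention estimate. Use the same form for the secondary scales; for PANAS-20 the two later visits are the first session and post-intervention. The analysis without baseline covariates then becomes a real comparison. The cost is SAP wording only, since the baseline scores are already collected.
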